## **9. STUDY ASSESSMENTS AND PROCEDURES**

### **9.1. Screening Assessments**

#### **9.1.1. Demographic and Medical History**

A complete medical history and review of body systems along with demographic data will be documented for all subjects during the screening period. All data up to the time of enrollment will also be recorded in the eCRF.

Any AE or change in the subject's condition or health status occurring after consent but prior to the first application of study drug will be recorded but not considered treatment emergent.

#### **9.1.2. Tumor Biopsy**

Tumor biopsy will be performed for subjects at Screening who do not have histologically confirmed TGCT. Any required biopsies should be performed after MRI review of the tumor by the central reader.

Tumor biopsy will be done via needle aspiration under CT or ultrasound guidance.

## **9.2. Efficacy Assessments**

#### **9.2.1. Tumor Assessment**

Overall Response (OR) will be centrally assessed from MRI scans using RECIST v1.1 ([Eisenhauer, 2009](#)). A complete response (CR) is defined as disappearance of all tumors, and a partial response (PR) is defined as at least a 30% decrease in the sum of diameters of target tumors from the baseline sum of diameters.

#### **9.2.2. MRI**

A separate MRI Manual will be provided detailing MRI procedures. MRIs will be read and evaluated by a central independent blinded reader for assessment of tumor response.

TVS is a semi-quantitative MRI scoring system that describes tumor mass and is based on 10% increments in the estimated volume of the maximally distended synovial cavity or tendon sheath involved. A score of 0 indicates no evidence of tumor; a score of 10 indicates a tumor that is equal in volume to that of a maximally distended synovial cavity or tendon sheath. The overall number of responses and the number of subjects with and without disease progression will be assessed.

## **9.3. Clinical Outcome Assessments**

Clinical outcome assessments will include Worst Pain NRS, Worst Stiffness NRS, PROMIS Physical Function Scale, BPI, and evaluation of joint ROM.

#### **9.3.1. Worst Stiffness NRS**

This is a single item self-administered questionnaire designed to assess “worst” stiffness at the site of the tumor. This instrument uses an 11-point NRS, ranging from 0 (“no stiffness”) to 10

(“worst stiffness imaginable”) (see [Appendix 1](#)). Subjects will be asked to recall their “worst” stiffness at the site of the tumor in the past 24 hours. Subjects will complete this assessment at Screening, Baseline (Week 0), Week 6, Week 12, and Week 14/ET.

### **9.3.2. PROMIS**

The PROMIS Physical Function Scale will be used to assess physical function of the upper and lower limbs (see [Appendix 2](#)). The scale ranges from 1 ('unable to do' or 'cannot do') to 5 ('without any difficulty' or 'not at all'), where higher scores represent better outcomes.

### **9.3.3. BPI**

The BPI Short Form is a self-administered questionnaire used to evaluate the severity of a subject's pain and the impact of this pain on the subject's daily functioning (see [Appendix 3](#)). The subject is asked to rate their worst, least, average, and current pain intensity, list current treatments and their perceived effectiveness, and rate the degree that pain interferes with general activity, mood, walking ability, normal work, relations with other persons, sleep, and enjoyment of life on a scale from 0-10.

### **9.3.4. EQ-5D-5L Health Assessment**

The EQ-5D-5L assessment is a widely used quality of life instrument that includes questions in each of 5 domains: mobility, self-care, usual activities, pain/discomfort, and anxiety/depression. The choices include 5 levels of severity for each domain followed by a general health VAS (see [Appendix 4](#)).

### **9.3.5. ROM**

ROM of the joint will be assessed by qualified assessors at the clinical site. Measurements will be recorded in degrees. At baseline, the plane of movement with the smallest (worst) relative value will be identified; only this plane will be used for evaluating change in ROM subsequently.

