	

2. TVS is a semi-quantitative MRI scoring system that describes tumor mass and is based on 10% increments in the estimated volume of the maximally distended synovial cavity or tendon sheath involved. A score of 0 indicates no evidence of tumor; a score of 10 indicates a tumor that is equal in volume to that of a maximally distended synovial cavity or tendon sheath. The overall number of responses and the number of subjects with and without disease progression will be assessed.

3. ROM of the joint will be assessed by qualified assessors at the clinical site. Measurements will be recorded in degrees. At baseline, the plane of movement with the smallest (worst) relative value will be identified; only this plane will be used for evaluating change in ROM subsequently.

4. The PROMIS Physical Function Scale will be used to assess physical function of the upper and lower limbs. The scale ranges from 1 ('unable to do' or 'cannot do') to 5 ('without any difficulty' or 'not at all'), where higher scores represent better outcomes.

5. The Worst Stiffness NRS is a 1-item, self-administered questionnaire assessing the "worst" stiffness within the last 24 hours. The NRS for this item ranges from 0 (no stiffness) to 10 (stiffness as bad as you can imagine).

6. The Worst Pain NRS is a component of the Brief Pain Inventory assessing the "worst" pain in the last 24 hours. The NRS for this item ranges from 0 (no pain) to 10 (pain as bad as you can imagine).

7. Brief Pain Inventory (BPI) Short Form is a self-administered questionnaire used to evaluate the severity of a subject's pain and the impact of this pain on the subject's daily functioning. The subject is asked to rate their worst, least, average, and current pain intensity, list current treatments and their perceived effectiveness, and rate the degree that pain interferes with general activity, mood, walking ability, normal work, relations with other persons, sleep, and enjoyment of life on a scale from 0 to 10.

8. EQ-5D-5L is a widely used quality of life instrument that includes questions in each of 5 domains: mobility, self-care, usual activities, pain/discomfort, and anxiety/depression. The choices include 5 levels of severity for each domain followed by a general health visual analogue scale (VAS).

--	--

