#### **3.2. Secondary Endpoints**

1. The proportion of subjects who achieve an overall tumor response (objective response [OR], which includes both complete response [CR] and partial response [PR]), per the Response Evaluation Criteria in Solid Tumors Version 1.1 (RECIST v1.1) ([Eisenhauer, 2009](#)) at Week 12
2. Proportion of subjects with overall response based on TVS, a TGCT-specific method that calculates tumor volume as a percentage of the estimated maximally distended synovial activity
3. Mean change from Baseline in ROM score
4. Mean change from Baseline in the PROMIS Physical Function score
5. Mean change from Baseline in Worst Stiffness NRS score
6. Percentage of subjects who respond with a decrease of at least 30% in mean BPI score
7. Mean change from Baseline in BPI
8. Mean change from Baseline in Worst Pain NRS score
9. EQ-5D-5L Health Assessment
10. Serum and synovial CSF1 levels
11. Serum and synovial AMB-05X levels
12. Serum and synovial anti-AMB-05X antibody levels

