### 6.1. Visit 1 / Screening

After the subject provides signed consent and HIPAA authorization (if applicable), the following procedures should be completed. Note that if necessary, screening assessments may be performed at more than one visit during the 4-week screening period.

- Assign a Subject ID. Each subject will be assigned a 6-digit Subject ID that consists of a 3-digit number representing the study site and a 3-digit subject number, sequential within each study site.
  - Thus, if the center number is 101, Subject IDs will be assigned as 101-001, 101-002, 101-003, etc., in ascending order. If the center number is 202, the Subject IDs will be 202-001, 202-002, 202-003, etc., in ascending order.
- Collect demographic information and take medical history.
- Record all concomitant medications, including dose amount and dosing frequency, taken within 4 weeks prior to Screening.
- Measure vital signs (blood pressure, heart rate, temperature, and respiratory rate) with subject in a sitting position after having rested for 5 minutes.
- Conduct a full physical examination (including height and weight).
- Perform a 12-lead ECG.
- Collect blood samples for clinical laboratory tests (chemistry and hematology), HBV, HCV, HIV, TB (QuantiFERON), and serum pregnancy test for females of childbearing potential.
- Collect a urine sample for urinalysis and urine drug screen.
- Perform MRI.
- Tumor assessment.
- Tumor biopsy for subjects who do not have histologically confirmed TGCT. Any required biopsies should be performed after MRI review of the tumor by the central reader.
- Perform the following clinical assessments:
  - Worst stiffness NRS
  - PROMIS Physical Function Scale
  - BPI
  - EQ-5D-5L
  - Joint ROM
- Review results and confirm eligibility.

Individuals who successfully complete Screening procedures and meet all eligibility criteria may be enrolled in the study. These subjects will be notified and scheduled for Visit 2 (Baseline). The interval between Visit 1 (Screening) and Visit 2 (Baseline) should not exceed 4 weeks.

For any subject who does not meet study eligibility criteria, capture screen failure information, report screen failure status, and record any changes in concomitant medications and AEs since Screening.

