## **6.2. Visit 2 / Baseline (Day 1, Week 0)**

### **6.2.1. Visit 2 – Pre-dose Procedures**

Confirm that subject meets all inclusion/exclusion criteria, then complete the following procedures prior to administration of first dose of study drug:

- Perform a urine pregnancy test for female subjects of childbearing potential.
  - Any subject with a positive result will be recorded as a screen failure.
- Collect a urine sample for urinalysis and urine drug screen.
- Update any changes in concomitant medications since Visit 1 (Screening).
- Record any AEs that may have occurred since the subject signed the ICF. AEs that occur before the first application of study drug will be recorded as such to distinguish them from TEAEs.
- Conduct a full physical exam and document any changes since the previous visit.
- Obtain weight.
- Measure vital signs (blood pressure, heart rate, temperature, and respiratory rate) with the subject in a sitting position after having rested for 5 minutes.
- Perform a 12-lead ECG.
- Collect blood samples for clinical laboratory tests (chemistry and hematology).
- Collect serum samples prior to dosing for measurement of AMB-05X concentration, CSF1 levels, and anti-AMB-05X antibodies.
- Collect synovial fluid for measurement of AMB-05X concentration, CSF1 levels, and anti-AMB-05X antibodies.
- Perform the following clinical assessments:
  - Worst stiffness NRS
  - PROMIS Physical Function Scale
  - BPI
  - EQ-5D-5L
  - Joint ROM

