## **10. STATISTICS**

### **10.1. General Considerations**

All study data will be summarized by treatment using descriptive statistics. Unless otherwise specified, descriptive statistics for numeric data (e.g., age, weight) will include the number of subjects with data to be summarized (n), mean, standard deviation (SD), median, minimum, and maximum. Categorical/qualitative data (e.g., sex, race) will be presented using absolute and relative frequency counts and percentages. All summaries, statistical analyses, and individual subject data listings described below will be completed using Version 9.3 or later of SAS software (SAS Institute, Inc., Cary, North Carolina).

A detailed final SAP will be provided separately. The SAP will be finalized prior to the first DMC meeting.

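### Where a subject's knee planes are close in relative value, choosing the worst plane and measuring change from what is most naturally the same Visit 2 reading biases mean ROM change toward improvement

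*Combined protocol and SAP*

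**What the plan says.** Section 9.3.5 gives the baseline rule: "the plane of movement with the smallest (worst) relative value will be identified; only this plane will be used for evaluating change in ROM". The synopsis (Section 1.1) repeats it: "only this plane will be used for evaluating change in ROM subsequently". Secondary endpoint 3 in Section 3.2 is "Mean change from Baseline in ROM score".

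Section 6.2 calls Visit 2 Baseline (Day 1, Week 0). Section 6.2.1 tells sites to "complete the following procedures prior to administration of first dose of study drug", and Joint ROM is on that list. ROM is also read at Visit 1 (Section 6.1), where "The interval between Visit 1 (Screening) and Visit 2 (Baseline) should not exceed 4 weeks". The protocol gives the Visit 1 reading no role in selecting the plane or in the change score.

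Section 9.3.5 records ROM in degrees. It does not list the knee planes, define relative value or name the visit at which the plane is chosen. Section 10.3 summarises efficacy endpoints descriptively with 95% confidence intervals and allows exploratory tests at 0.05 without multiplicity adjustment. On further detail, Section 10.1 says "A detailed final SAP will be provided separately"; that SAP is not among the documents reviewed.

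**The concern.** Taking the lowest of several noisy readings tends to pick one whose error happened to be negative. A later reading in the same plane does not carry all of that error, so it is expected to be higher even if nothing has changed. If the selecting reading is also the comparator, this regression to the mean goes straight into the change score, always in the direction of improvement. The study has a single open-label arm, so no control group shows the same drift.

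At stake is the mean ROM change and its confidence interval: with about 12 subjects, a small built-in shift could be read as early functional benefit. The primary endpoint (TEAEs) is untouched, and no stated decision rule uses a ROM threshold.

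**Working it through.** **Which reading selects the plane.** Section 9.3.5 says only that this happens at baseline.

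- For Visit 2: Section 6.2 names that visit Baseline, and Section 9.3.1 keeps Screening and Baseline apart ("Subjects will complete this assessment at Screening, Baseline (Week 0), Week 6, Week 12, and Week 14/ET").
- Against certainty: Section 9.2.1 defines partial response as "at least a 30% decrease in the sum of diameters of target tumors from the baseline sum of diameters", yet the only MRI before dosing is at Screening. Lower-case baseline is therefore not always Visit 2.

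Visit 2 is the more natural reading, but it is an inference.

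**Inputs.** From the documents: about 12 subjects, no control arm, ROM read at Visits 1 and 2, 95% CI. Assumed, because the documents give nothing: two planes, normal errors with SD 1 per reading, between-plane error correlation ρ, true gap g between planes in error SDs, and no mean change. There is no ROM figure in the plan to reproduce.

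**Formula.** With errors independent across visits, the difference between the two planes' errors has SD s = √(2(1−ρ)). The expected error of the selected (lower) reading is −s·φ(g/s), where φ is the standard normal density. The follow-up error averages zero, so

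bias in change = s·φ(g/s).

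- ρ = 0.5 gives s = 1. Bias is φ(0) = 0.399, φ(1) = 0.242, φ(2) = 0.054.
- ρ = 0 and g = 0 gives √2 × 0.399 = 0.564.
- If gaps vary across subjects as normal with mean 0 and SD 3, ρ = 0.5, the average of φ(g) is 0.399/√(1+9) = 0.126. Simulation gives 0.12 to 0.13.

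**Effect on the interval.** Simulated shares of null trials with n = 12 in which the t-based 95% CI lies wholly above zero, with no between-subject variation in true change (nominal 2.5%):

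| Setting | Bias (error SD) | CI wholly above zero |
|---|---|---|
| One plane | 0 | 2.5% |
| Gap 2 SD, ρ 0.5 | 0.05 | 3% |
| Gaps varying with SD 3, ρ 0.5 | about 0.12 | about 4.7% |
| Gap 1 SD, ρ 0.5 | 0.24 | 8% |
| Tied in every subject, ρ 0.5 | 0.40 | 15% |
| Tied in every subject, ρ 0 | 0.56 | about 28% |

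If true change also varies between subjects with SD 2, the bias is the same but the shares fall: 15% to 7.5%, 28% to 11%, and the varying-gap case to 3.5%.

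**Other assumptions.**

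- If Visit 2 and follow-up errors are correlated r2f, the bias is multiplied by (1 − r2f). For tied planes, ρ 0.5 and r2f 0.5: 0.399 × 0.5 = 0.20.
- If selection uses relative value, change is in degrees and the reference ranges differ 2:1 or 3:1, the tied-plane bias at ρ 0.5 is 0.35 or 0.30.
- Three tied planes with uncorrelated errors would give 0.85, so the last table row is the ceiling of the two-plane model only.

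**Separating the two readings.** Let b be the bias under independent visits. Selecting on Visit 1 and measuring change from Visit 2 gives b·(r12 − r1f), where r12 and r1f are the correlations of the Visit 1 error with the Visit 2 and follow-up errors. For tied planes and ρ 0.5:

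- r12 = r1f = r2f = 0.5: 0.20 falls to 0.
- r12 = 0.5, r1f = r2f = 0.3: 0.399 × 0.7 = 0.28 falls to 0.399 × 0.2 = 0.08.
- r12 = 0.5, r1f = r2f = 0: 0.40 falls to 0.399 × 0.5 = 0.20.

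**The case against.** The strongest objection is that the triggering condition is not shown. Enrolment is limited to the knee, no section lists two or more planes, and some neighbouring text is not knee-specific (tendon sheaths in Section 9.2.2, upper limbs in Section 9.3.2). The worst-plane rule may be generic wording with little selecting to do here. This stands as a limit on size. It does not dispose of the point, because the rule has content only if planes are compared, and whenever close planes are compared on the comparator reading the bias follows.

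Second, nothing says in terms that the Visit 2 reading does both jobs, and the separate SAP may already split them. Both are correct, and the conclusion is conditional on them.

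Third, fixing one plane in advance prevents a favourable plane from being picked afterwards. That is a real merit, and separate readings would keep it.

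A reader might infer from the tied-plane rows that this trial has a 15% or 28% chance of a spuriously positive ROM result. The documents do not support that: those figures need exactly tied planes in all 12 subjects and no variation in true change. Nor do they support reading the point as a demonstrated bias of known size in degrees.

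**Conclusion.** The point holds in conditional form. On the natural reading of Sections 1.1, 3.2, 6.2 and 9.3.5, one Visit 2 reading selects the plane and anchors the change, and where planes compete the mean change leans toward improvement. A plausible size under the assumed two-plane model (ρ 0.5, independent visits) is 0.05 to 0.24 error SD, with about 3% to 8% of null trials showing an interval wholly above zero. It is about zero with one plane or a clearly worst plane.

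The consequence is small: one of 12 secondary outcomes, summarised descriptively. The missing control arm already limits any drug-effect reading of ROM; this adds a bias that readings already scheduled can remove or reduce. If the SAP separates the two readings, the point is met.

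**What to change.** In Sections 1.1 and 9.3.5 and in the SAP:

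- list the knee planes measured and define relative value;
- select the plane from the Visit 1 (Screening) ROM reading;
- compute change from the Visit 2 pre-dose reading in that plane;
- report change in all measured planes alongside, as a summary free of selection bias.

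The cost is two or three sentences and a few extra outputs, with no new measurement. There are two downsides. Up to 4 weeks, and possibly a biopsy, fall between the visits, so the selected plane may not be the worst at Visit 2. Some bias also remains if Visit 1 errors are more alike with Visit 2 than with follow-up; the all-plane summary covers that case.

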## **9.4. Pharmacokinetic/Pharmacodynamic Assessments**

Serum AMB-05X concentrations will be measured at Week 0 (pre-dose and 2 hours after the first dose), Week 2 (pre-dose [trough]), and Week 10 during steady state (including pre-dose [trough] and 2 hour after the last dose). Synovial AMB-05X concentrations will be measured pre-dose at Weeks 0, 2, 4, 6, 8, and 10.

Serum CSF1 levels will be measured at Week 0 (including pre-dose and 2 hours after first dose), Week 2 (pre-dose [trough]), and Week 10 during steady state (including pre-dose [trough] and 2 hours after the last dose). Synovial CSF1 levels will be measured pre-dose at Weeks 0, 2, 4, 6, 8, and 10. CSF1 will be measured by ELISA analysis.

Serum anti-AMB-05X antibody levels will be measured pre-dose at Week 0 and at Week 10. Synovial anti-AMB-05X antibody levels will be measured pre-dose at Weeks 0, 4, and 10.

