## 1.2. Study Schema

### 1.3. Schedule of Events

Study Visit	Screening		Treatment Period							Follow-up	
	V1 Screening	V2 Baseline	V3	V4	V5	V6	V7	V8/ET	V9	V10	
Study Week	≤4 weeks before Baseline	0	2	4	6	8	10	12	14	24	
Study Day	Baseline	1	15 ± 2	29 ± 2	43 ± 3	57 ± 3	71 ± 3	85 ± 3	99 ± 3	169 ± 7	
ICF/HIPAA	X										
Assign Subject ID	X										
Demographic data	X										
Medical history	X										
Inclusion/exclusion criteria	X										
Confirmation of eligibility	X	X									
Physical exam	X	X			X			X	X	X	
Weight and height 	X	X	X	X	X	X	X	X	X	X	
Vital signs 	X	X	X	X	X	X	X	X	X	X	
12-lead ECG	X	X			X					X	
Pregnancy test 	X	X		X		X					
Urine drug screen	X	X									
Clinical laboratory tests 	X	X			X			X		X	
HBV, HCV, HIV, TB	X										
Serum PK samples 		X	X				X				
Serum CSF1 		X	X				X				
Serum anti-AMB-05X antibody 		X					X				
Synovial PK samples 		X	X	X	X	X	X				
Synovial CSF1 		X	X	X	X	X	X				
Synovial anti-AMB-05X antibody 		X		X				X			

 Height is collected only at the Screening.

 Vital signs consist of blood pressure, heart rate, temperature, and respiratory rate measured with the subject in a sitting position after having rested for 5 minutes.

 For females of childbearing potential, a serum pregnancy test will be performed at Screening and a urine pregnancy test will be performed at subsequent visits indicated.

 Clinical laboratory tests to include chemistry, hematology, and urinalysis

 Serum samples will be collected for measurement of AMB-05X concentrations pre-dose and 2 hours post-dose at Week 0, pre-dose at Week 2, and pre-dose and 2 hours post-dose at Week 10.

Serum CSF1 levels will be measured at the same timepoints.

Serum anti-AMB-05X antibody will be measured in the pre-dose samples at Week 0 and Week 10.

 Synovial fluid (2 mL) will be collected pre-dose at Weeks 0, 2, 4, 6, 8, and 10 for AMB-05X PK measurements, and for CSF1. Synovial anti-AMB-05X antibody will be measured in the pre-dose samples at Week 0 and Week 4, and at Week 10.

Study Visit	Screening		Treatment Period							Follow-up	
	V1 Screening	V2 Baseline	V3	V4	V5	V6	V7	V8/ET	V9	V10	
Study Week	≤4 weeks before Baseline	0	2	4	6	8	10	12	14	24	
Study Day	Baseline	1	15 ± 2	29 ± 2	43 ± 3	57 ± 3	71 ± 3	85 ± 3	99 ± 3	169 ± 7	
MRI 	X				X			X		X	

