#### **2.3.4. Non-Human Primate Intra-articular Administration of AMB-05X**

The clinical formulation of AMB-05X was sequentially injected at two dose levels into the knees of 4 normal male 6-10 kg cynomolgus monkeys (AMB051-20-NHP1 CRL-Reno). On Day 1, anesthetized animals received a dose of 1.5 mg/kg (a human-equivalent dose of ~100 mg), 0.035 mL/kg and a time-course of serum sampling was performed over the following week and the injected knee was sampled for synovial drug levels on Day 8. Three weeks after the first IA administration, the protocol called for injection of the other knee at 5 mg/kg (█ mL/kg of the █/mL AMB-05X formulation), but the animals were inadvertently dosed at ~0.04 mL/kg again and hence, ~2.5 mg/kg or a human equivalent of ~160 mg. Serum sampling was performed at various time points over a two-week period and synovial drug levels were analyzed one- and two-weeks post dosing. Clinical observations and animal mobility were assessed daily and knee range-of-motion testing was performed on both knees (i.e. with and without AMB-05X dosing) was performed on Days 2 and 7 of each dosing cycle. Food consumption and body weights were additionally monitored. Regardless of the administered dose or time point of examination, there were no observations of abnormal behavior, mobility, or altered knee range of motion measurements. AMB-05X drug levels were generally consistent with modeled projections and was generally linear between the two dose levels. For example, at the █ mg/kg IA dose, the serum AMB-05X  $C_{max}$  was █ µg/mL (mean  $\pm$  SD) and declined to █ µg/mL over the week following dosing. Following the second dosing interval (~2.5 mg/kg), two of four animals had serum and synovial drug levels approximately linearly increased from the 1.5 mg/kg dose and 2 had very low synovial and systemic exposures, potentially related to ADA and currently under investigation. Serum  $AUC_{last}$  values averaged █ µg·hr/mL at █ mg/kg and █ µg·hr/mL at █ mg/kg (for the two animals with substantial exposures). The knee synovial fluid AMB-05X concentration 7 days post-dose was █ µg/mL (█ nM) for both dose levels.

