#### **2.4.1.2. Combination Study with Pembrolizumab**

The primary objective of Study 20150195 was to evaluate the safety, tolerability, and objective response rate (ORR) of AMB-05X administered in combination with pembrolizumab in subjects with select advanced solid tumors.

This study was conducted in 2 parts. Part 1 (phase 1b) evaluated the safety of AMB-05X in combination with pembrolizumab using a 6+3 design. The starting dose was 1400 mg AMB-05X plus 200 mg pembrolizumab every 3 weeks (Q3W). Part 2 (phase 2) further evaluated the safety and tested whether AMB-05X could enhance the antitumor activity observed historically with pembrolizumab alone and/or overcome lack of response to pembrolizumab monotherapy in subjects with select solid tumors.

A total of 15 subjects were enrolled in part 1 of the study, all of whom received  $\geq$  1 dose of AMB-05X and pembrolizumab. Subjects were treated with AMB-05X and pembrolizumab for a mean (SD) of 0.8 (0.7) months. In part 2 of the study, 101 subjects were enrolled all of whom received  $\geq$  1 dose of AMB-05X and pembrolizumab. Ninety (90) subjects received AMB-05X 1100 mg every 3 weeks plus pembrolizumab 200 mg every 3 weeks and 11 subjects received AMB-05X 1400 mg every 3 weeks plus pembrolizumab 200 mg every 3 weeks. Subjects were treated with AMB-05X and pembrolizumab for a mean (SD) of 1.6 (2.5) months.

The objective response rate was 0% in Part 1 and 3.0% in Part 2.

PK results from a total of 116 subjects were available from the study. Following administration in cycles 1 and 2, AMB-05X exposures increased in an approximately dose-proportional manner over the dose range of 1100 to 1400 mg. Mean  $C_{max}$  and mean AUC over the dosing interval  $\tau$  ( $AUC_\tau$ ) increased by 1.4- and 1.5-fold, respectively, in cycle 1 and 1.4-fold and 1.5-fold, respectively, in cycle 2, for a 1.3-fold increase in dose. Median time to reach  $C_{max}$  ( $t_{max}$ ) values ranged from 2.0 to 3.0 hours postdose in cycles 1 and 2. No significant serum accumulation of

AMB-05X was observed in subjects between cycles 1 and 2 with mean accumulation ratio for AUCτ ranging from 1.25 to 1.27.

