Serum anti-AMB-05X antibody levels will be measured pre-dose at Week 0 and Week 10. Synovial anti-AMB-05X antibody levels will be measured pre-dose at Weeks 0, 4, and 10.

Safety, PK, PD, and efficacy assessments will be reviewed by the Sponsor on a continuous, subject-by-subject basis to determine whether the assigned dose is appropriate. Depending on these results, the Sponsor may either decrease the dosage strength to 90 mg or increase the dosage strength to 210 mg in subsequent subjects who enroll. In general, subjects are expected to complete the study at the dose strength which they started the study, unless they experience a clinically significant AE that would warrant a dose reduction. As a general rule, clinically

significant AEs include, but are not limited to, any AE considered to be at least possibly related to study drug and severe in intensity or meets the criteria for a SAE. Subjects who are unable to tolerate a dosage strength of 90 mg will be withdrawn from the study

When at least 3 subjects have completed Week 6, a data monitoring committee (DMC) will review the available safety, tolerability, PK, PD, and efficacy data. Study enrollment and conduct may continue unchanged during DMC review. Based on the recommendations of the DMC, the Sponsor may then implement any one of the following adaptive changes without a protocol amendment:

- Continuation of enrollment under the existing design, without any changes to the study.
- Continuation of enrollment with a new dose or dose frequency criteria. Specifically, the DMC may recommend a dose reduction to 90 mg or a dose increase to 210 mg in subsequent subjects. Subjects may not exceed a dose of 210 mg or go below a dose of 90 mg. Subjects who are unable to tolerate a dose of 90 mg will be discontinued from the study.
- Discontinuation of further enrollment and/or suspension/termination of the study

Thereafter, the DMC should continue to review available data on a regular basis throughout the study (each time 3 subjects complete study treatment) and provide ongoing recommendations regarding appropriate next steps in study conduct (as outlined above). If a change in dose is made during the study, the DMC will again review the available data when 3 subjects have completed Week 6 at the new dose and provide further recommendations as outlined above.

[figure not shown]
Refer to [Appendix 5](#) for potential changes to study conduct in the context of COVID-19 (coronavirus disease 2019).

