### **6.5. Visit 5 (Week 6 ± 3 days)**

Complete the following procedures during the visit:

- Record any changes in concomitant medications since the previous visit.

- Record any AEs that may have occurred since the previous visit and follow up on the status of any existing AEs.
- Conduct a full physical exam and document any changes since the previous visit.
- Measure vital signs (blood pressure, heart rate, temperature, and respiratory rate) with the subject in a sitting position after having rested for 5 minutes.
- Obtain weight.
- Perform a 12-lead ECG.
- Collect a urine sample for urinalysis.
- Collect blood samples for clinical laboratory tests (chemistry and hematology).
- Collect synovial fluid for measurement of AMB-05X concentration and CSF1 levels prior to study drug injection.
- Perform MRI.
- Tumor assessment.
- Perform the following clinical assessments:
  - Worst stiffness NRS
  - PROMIS Physical Function Scale
  - BPI
  - EQ-5D-5L
  - Joint ROM
- Inject study drug.
- Observe subject for a minimum of 90 minutes after dosing to monitor for any adverse reactions, including any injection-site reactions.

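### The Week 6 DMC look, which can lead to a dose change, is guaranteed serum drug and CSF1 data from the first dosing interval only

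*Combined protocol and SAP*

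**What the plan says.** Section 9.4 of the protocol fixes the serum schedule: "Serum AMB-05X concentrations will be measured at Week 0 (pre-dose and 2 hours after the first dose), Week 2 (pre-dose [trough]), and Week 10" for the drug and "Serum CSF1 levels will be measured at Week 0 (including pre-dose and 2 hours after first dose), Week 2 (pre-dose [trough]), and Week 10" for the biomarker. The footnote to the Schedule of Events (Section 1.3) agrees, giving "pre-dose and 2 hours post-dose at Week 0, pre-dose at Week 2, and pre-dose and 2 hours post-dose at Week 10", and so do the visit lists in Sections 6.2 to 6.7. Visits 4, 5 and 6 (Weeks 4, 6 and 8) have no serum drug or CSF1 sample. At Week 6 the visit list asks staff to "Collect blood samples for clinical laboratory tests (chemistry and hematology"), with no aliquot for PK or CSF1.

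Section 4.1 sets the decision point. Once at least three subjects have finished Week 6, "a data monitoring committee (DMC) will review the available safety, tolerability, PK, PD, and efficacy data". The dose may then move to 90 mg or 210 mg in subsequent subjects without an amendment. If it moves, "the DMC will again review the available data when 3 subjects have completed Week 6 at the new dose". Further looks follow each time three subjects finish treatment.

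Synovial drug and CSF1 are sampled before every injection, and synovial anti-drug antibody at Weeks 0, 4 and 10. Serum anti-drug antibody is taken at Weeks 0 and 10 only.

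**The concern.** The look is timed at Week 6 and is meant to weigh PK and PD, but the serum schedule skips from Week 2 to Week 10. The Week 2 sample is taken before the second injection, so for a subject who has just finished Week 6 no serum value reflects any injection after the first. The same holds at the repeat look after a dose change.

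The missing compartment matters because the systemic safety argument in Section 2.3.5 is made in serum: low serum exposure relative to the exposures at which transaminases rose in the intravenous monotherapy study. Synovial troughs do not speak to that argument under repeat dosing. A recommendation on dose could therefore be made, and made again at the new dose, with no measurement of how far serum levels have built up or how serum CSF1 has responded.

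**Working it through.** The plan states no accumulation figure for the intra-articular route, so there is none to reproduce. The check has three steps.

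**1. Schedule set beside the trigger** (Sections 1.3, 6.2 to 6.7 and 9.4)

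| Week | Injection | Serum drug and CSF1 | Synovial drug and CSF1 | Chemistry |
|---|---|---|---|---|
| 0 | 1st | pre-dose, 2 h | pre-dose | yes |
| 2 | 2nd | pre-dose | pre-dose | no |
| 4 | 3rd | none | pre-dose | no |
| 6 | 4th | none | pre-dose | yes |
| 8 | 5th | none | pre-dose | no |
| 10 | 6th | pre-dose, 2 h | pre-dose | no |

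Through Week 6 a subject has 2 + 1 = 3 serum samples, 4 synovial samples and 4 injections. Only one injection precedes the latest serum sample. The serum gap is 10 − 2 = 8 weeks and spans three dosing visits (Weeks 4, 6 and 8).

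**2. Could Week 10 serum already exist at the look?**

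Week 6 is Day 43 and Week 10 is Day 71, each ± 3 days. The distance is 28 days, or from 68 − 46 = 22 to 74 − 40 = 34 with the windows. If the look falls when the third subject finishes Week 6, the first subject must be about 28 days ahead of the third to have Week 10 serum. The documents give no accrual rate. Assuming Poisson accrual, with x = 28 × (subjects per month)/30.4, the probability is e^(−x)(1 + x):

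- 1 subject per month: 0.77
- 2 per month: 0.45
- 3 per month: 0.24
- 4 per month: 0.12

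So later serum may be available from one subject, but nothing in the plan requires it.

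**3. What the missing trough might show (illustration)**

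The only human accumulation figure is in Section 2.4.1.2: a mean ratio for AUC over the dosing interval between cycles 1 and 2 "ranging from 1.25 to 1.27", for intravenous dosing every 3 weeks. Assume one-compartment linear kinetics and let r21 and r14 be the fractions remaining after 21 and 14 days.

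- Ratio = 1 + r21, so r21 = 0.25 to 0.27.
- Half-life = 21 × ln 2 / (−ln r21) = 10.5 to 11.1 days.
- r14 = r21^(14/21) = 0.397 to 0.418.
- Week 6 trough / Week 2 trough = 1 + r14 + r14² = 1.55 to 1.59.

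For assumed half-lives of 3, 5, 7 and 14 days the same ratio is 1.04, 1.16, 1.31 and 1.75. For scale, the step from 150 to 210 mg is 210/150 = 1.40.

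**The case against.** Much of the case on the other side stands.

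- **A reader might infer that the DMC sees nothing but first-interval serum.** The documents do not support that. The trigger is a minimum of three subjects and the review covers whatever data are available, so an early subject may already have Week 10 serum. Later looks will include it.
- **A reader might infer that loss of exposure on repeat dosing would stay hidden.** Section 2.3.4 reports that after the second injection "2 had very low synovial and systemic exposures, potentially related to ADA" in a group of four monkeys. That fall was synovial as well as systemic. A similar fall here would probably show in the synovial troughs at Weeks 2, 4 and 6, backed by synovial anti-drug antibody at Week 4. The animals were also injected in the other knee, three weeks later and at a different dose, which is not the trial's regimen.
- **A reader might doubt the steady-state label at Week 10.** Under the model above, the trough after five doses is 1 − r14⁵, about 99% of steady state, and still about 97% at a 14-day half-life. The label is reasonable.
- **Liver safety is observed directly.** Chemistry at Week 6 follows three injections.
- **The 1.55 to 1.59 figure is weakly anchored.** It carries over intravenous doses of 1100 to 1400 mg given with pembrolizumab, and the protocol does not regard that ratio as significant accumulation. Section 2.3.2 reports nonlinear kinetics in monkeys at 0.1 to 5 mg/kg, and no accumulation beyond 2-fold on weekly dosing.
- **One trough is not an AUC.** Section 2.3.5 frames its margin in AUC units, so a Week 6 trough cannot test that margin directly.

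What remains is that repeat-dose serum exposure and serum PD are not guaranteed at either Week 6 look, and that synovial or chemistry data do not measure them.

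**Conclusion.** The point holds in a limited form. The serum schedule is consistent throughout the protocol, but it does not match the timing of the dose look: each subject just finishing Week 6 brings three serum samples, all from the first dosing interval, after four injections. The gap is systemic only, because local exposure and liver safety are partly covered.

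The sample counts need no assumption. The size of the unseen change does: 1.55 to 1.59 if the intravenous ratio carries over under one-compartment linear kinetics, and 1.04 to 1.75 across assumed half-lives of 3 to 14 days. The low end is essentially no accumulation, and intra-articular kinetics may differ from all of these. The documents do not allow anyone to say that an unseen rise of this size would matter clinically, and no dose or dosing rule is judged here. This is a cheap improvement to the data behind a decision, not an error that undermines the trial.

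**What to change.** In the Schedule of Events (Section 1.3), Section 6.5 and Section 9.4, add a pre-dose serum aliquot for AMB-05X and CSF1 at Visit 5 (Week 6), taken from the venipuncture already made for chemistry and hematology. Make the matching edits to the Section 4.1 sampling text, the PK text in the synopsis and the laboratory manual. In the DMC package for the first Week 6 look, and for the repeat look after any dose change, list each subject's Week 2 and Week 6 serum troughs side by side, next to the synovial troughs.

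The cost is a few mL of blood per subject, about 12 drug assays and 12 CSF1 assays for the planned enrollment of approximately 12, and assay turnaround fast enough to report before the look. The sample gives a check on serum accumulation and a repeat-dose serum PD value; the package should say that it does not estimate AUC or peak.
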